Contact information is required to contact the subjects after the phone screening in case the research staff needs to reschedule Visit 1 or for follow up if the subject does not show for the Visit 1. Because this study is recruiting using mass email, subject information including a brief description why they were deemed ineligible (i.e. health history, medication, breastfeeding) will be kept to prevent making contact twice with an individual who is ineligible. Information on why a potential subject is ineligible/not passing the phone screening is to report to NIH and to monitor our recruiting progress. Information on how the subjects heard of the study will help the research team understand the most successful methods for advertising for the study.

VII.D.23 Will this information be shared with anyone outside the UI research team members?

No

VII.D.25 *After the subject agrees to participate (signs consent), are there any screening procedures, tests, or studies that need to be done to determine if the subject is eligible to continue participating?*

Yes

VII.D.26 *List and describe screening*

Complete the additional info survey (see attached RedCap document "additional info survey") for study records
 Medical history and physical exam
 Resting blood pressure and heart rate
 Standard blood chemistries (lipids, complete blood count, basic metabolic panel, liver enzymes)
 Urine pregnancy test

VII.D.27 *Discuss how much time a potential subject will have to agree to consider participation and whether or not they will be able to discuss the study with family/friends before deciding on participation.*

There is no time limit for the subject to agree to consider to be in the study as long as the study is actively recruiting subjects and they are still eligible. Subjects are allowed to discuss the study with family/friends before deciding on participation.

VII.D.28 *How long after the subject agrees to participate do study procedures begin?*

The procedures in visit 1 (screening visit) can occur on the same day as consent. The experimental visits (pickup and begin oral treatment) will begin within 1-2 weeks or less of visit 1.

VII.D.29 *Provide a description of the enrollment and consent process for adult subjects*

- *Describe each study population separately including control population*
- *Include when recruitment and consent materials are used*

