VII.E.2 *Describe randomization scheme/assignment including ratio such as 1:1, 2:1 etc.*
Subjects will be randomized to which treatment they receive first (placebo or losartan). All subjects will complete both arms of the study. They will be blinded to which treatment they are receiving at the time of the treatments. If they wish to know, subjects can be informed which treatment they received at what time when they complete the study.

VII.E.3 *Will any questionnaires, surveys, or written assessments be used to obtain data directly from subjects in this study?*
Yes

VII.E.4 *List all questionnaires, surveys, written assessments and ATTACH each one to the application. (NOTE: You are NOT prohibited from attaching copyrighted materials to this application)*
pre-consent screening survey
additional information survey
health history questionnaire

VII.E.5 *Does this project involve creating any audiotapes, videotapes, or photographs?*
No

VII.E.6 *Provide a detailed description in sequential order of the study procedures following the consent process - DO NOT cut and paste from the Consent Document.*

Describe study populations separately if they will be participating in different procedures - include CONTROL population if applicable.

DESCRIBE:

- *What subjects will be asked to do/what happens in the study (in sequential order)*
- *The time period over which procedures will occur*
- *The time commitment for the subject for individual visits/procedures*
- *Long-term followup and how it occurs*

Visit 1 - Consent and Screening (approximately 1 hour)

The PI or research staff explain the study and go over the informed consent with the participant. After the participant signs the informed consent, the PI or research staff performs the physical screening that includes urine pregnancy test, heart rate (HR), blood pressure (BP), height, waist circumference, and weight measurements. The participant fills out the health history questionnaire and confirms that they are using an effective form of birth control. A research nurse performs or approved laboratory personnel standard venipuncture to obtain blood (total = 7.5ml blood) for complete blood count (CBC), chemistry analysis, and lipid profile to be measured at UIHC pathology labs. The subject provides a urine sample for the measurement of urine proteins which will be measured by the UI Diagnostic Lab.

Visits 2 and 5- Pick up study medications (approximately 15 minutes)

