24-hour blood pressure measurement: There are no known or foreseeable risks associated with 24-hour blood pressure monitoring. The hourly cuff inflation may be disruptive to the participants activities of daily life. The cuff may cause mild pressure discomfort when inflating.

Pulse wave velocity (PWV): There are no known or foreseeable risks associated with the use of applanation tonometry for PWV. EKG patches are used for the monitoring and may cause minor skin irritation.

Losartan Pharmacotherapy: Losartan is a commonly prescribed hypertensive medication that works by blocking the angiotensin II type 1 receptors located on the vascular tissues. The most common but least serious side effects of losartan are cold symptoms (stuffy/runny nose, sneezing, sore throat), mild dizziness, back pain, and diarrhea.

Injury or death of unborn babies: Losartan is classified as pregnancy category D. Studies in pregnant women have demonstrated risk to the fetus. Pregnancy or planning to become pregnant are exclusion criteria in this study.

Low blood pressure (hypotension): Use of an anti-hypertensive medication may cause a decrease in blood pressure that leads to dizziness, faintness, or lightheadedness, especially when going from lying down to standing up. This can be treated by stopping the medication.

For people who already have kidney problems, losartan may lead to worsening of kidney function. Abnormal kidney function is an exclusion criteria for this study. We screen participants for markers of kidney function, and repeat those measurements (blood chemistry) at the end of each treatment period.

Swelling in feet, ankles, or hands, or unexplained weight gain: In some patients, losartan use may lead to edema. This can be treated by stopping the medication.

Allergic reaction: Subjects could have a mild or severe allergic reaction including hives; difficult breathing; swelling of the face, lips, tongue, or throat. We exclude subjects who have a known allergy to losartan.

Emotional or Psychological risks: There are no foreseeable psychological risks with this study.

Social Risks: There are no foreseeable social risks with this study

Legal Risks: There are no foreseeable legal risks with this study.

Loss of confidentiality is possible.

VIII.2

What have you done to minimize the risks?

- **If applicable to this study ALSO include:**
 - How you (members of your research team at Iowa) will monitor the safety of individual subjects.

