 - Include a description of the availability of medical or psychological resources that subjects might require as a consequence of participating in this research and how referral will occur if necessary (e.g. availability of emergency medical care, psychological counseling, etc.)

Note: All investigational substances used in these protocols are used with general Physician Oversight (see attached Standard Operating Procedures document)

Risks Associated with Losartan Treatment: Because of the risk of injury or death to unborn babies we perform a pregnancy test on all subjects before administering losartan and council participants on the risks of becoming pregnant while taking the medication. During the study if a subject experiences side effects that are life threatening, the subject will be instructed to call 911. If the subject experiences any mild but tolerable expected side effects such as cold symptoms, mild dizziness, back pain, or diarrhea, they will be asked to keep a log of these including the date, the duration, and the severity by rating on a scale of 1 (mild) to 10 (severe/intolerable). If the subject feels the side effects are uncomfortable or intolerable, then they will be instructed to call the Research Associate ([name]) or [name]. The Research Assistant or [name] (although she will be blinded) will instruct the subject to skip the next dose and if the symptoms/side effects have resolved at time of next dose (in 24 hours), they will be instructed to take the next dose. [name] will consult with [name] if necessary. If symptoms do not resolve or worsen at time of next scheduled dose, the subject will be instructed to discontinue the treatment. The subject will be withdrawn from the study procedures but will be followed up as necessary.

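### The schedule lists no pregnancy test before period 2, so women randomized to placebo first start losartan at least 8 to 10 weeks after their only listed test.

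*Combined protocol and SAP*

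**What the plan says.** The losartan risk section (VIII.1) names injury or death of unborn babies and states: "Losartan is classified as pregnancy category D. Studies in pregnant women have demonstrated risk to the fetus". Section VIII.2 gives the matching safeguard: "we perform a pregnancy test on all subjects before administering losartan", together with counselling. It names no visit, no interval and no repeat.

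The test appears in two places, both referring to the same occasion. The post-consent screening list (VII.D.26) includes "Urine pregnancy test", and the visit 1 description (VII.E.6) says staff "performs the physical screening that includes urine pregnancy test". At that visit the participant also "confirms that they are using an effective form of birth control". Oral treatment starts soon afterwards: the experimental phase "will begin within 1-2 weeks or less of visit 1" (VII.D.28).

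The later visits in VII.E.6 list no pregnancy test and no second contraception check:

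- Visits 2 and 5: medication is handed out with instructions.
- Visits 3 and 6: the blood pressure monitor is fitted.
- Visits 4 and 7: the experiments are done. The urine collected is for protein measurement.

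The order of treatments is randomized (VII.E.2). Each period lasts 6 weeks, with a washout of at least 14 days between them and no stated maximum. The end of VII.E.6 also allows the second-period pills to be handed out at the close of the first experimental visit, which is visit 4 in the seven-visit list.

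**The concern.** A pregnancy test informs only about the time up to and around when it is taken. In a crossover the drug may start in either period, so a single test at screening gives the two sequences different protection. Losartan-first women are tested shortly before exposure. Placebo-first women go through a whole treatment period and a washout before exposure, with no further test listed.

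The plan does specify repeat safety checks elsewhere. For kidney function, VIII.1 says staff "repeat those measurements (blood chemistry) at the end of each treatment period". There is no equivalent line for pregnancy, although the fetal risk is the reason VIII.2 gives for testing.

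The early hand-out option widens the gap. If period-2 pills are given at visit 4, visit 5 drops out. The next listed contact is then visit 6, one day before the final experimental visit. A placebo-first woman who conceived during placebo or washout could take losartan for essentially the full 6 weeks before any scheduled contact.

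This is a matter of participant and fetal safety. It does not affect the primary outcome, the analysis or the sample size.

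**Working it through.** The plan states no test-to-dose interval, so there is no figure to reproduce. The interval follows from the schedule.

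**Inputs from the document**

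| Input | Value | Section |
|---|---|---|
| Only listed pregnancy test | Visit 1, week 0 | VII.D.26, VII.E.6 |
| Lead-in from visit 1 to period 1, L | 0–2 weeks | VII.D.28 |
| Length of each period | 6 weeks | VII.E.6 |
| Washout | at least 2 weeks, no maximum | VII.E.6 |
| Planned total; expected screen failures; expected dropouts | 20; about 5; about 5 | XI.2 |

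**Age of the test at the first losartan dose**

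- Losartan first: L = 0 to 2 weeks.
- Placebo first, minimum washout: L + 6 + 2 = 8 weeks (L = 0) to 10 weeks (L = 2). It is longer if the washout exceeds 14 days.
- Placebo-first women finish losartan at L + 6 + 2 + 6 = 14 to 16 weeks after the test, again at minimum washout.

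**Likelihood of a pregnancy in the gap**

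This step needs two assumptions that are not in the documents: an annual contraceptive failure rate f of 1% to 10%, and 1:1 allocation. The probability per woman over w weeks is 1 − (1 − f)^(w/52).

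| f | w = 2 | w = 8 | w = 10 |
|---|---|---|---|
| 1% | 0.04% | 0.155% | 0.193% |
| 5% | – | 0.79% | 0.98% |
| 10% | 0.40% | 1.61% | 2.01% |

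At w = 0 the probability is 0, so the losartan-first range is 0 to 0.40%. The placebo-first range is 0.155% to 2.01%.

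**Expected number in the trial**

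- Enrolled after screening: 20 − 5 = 15. With up to 5 dropouts, 10 to 15 women reach period 2.
- With 1:1 allocation, about 5 to 8 of these are placebo-first.
- Low end: 5 × 0.155% = 0.008. High end: 8 × 2.01% = 0.16.

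**Calendar reach**

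This version is dated 7/19/2024 and the last intervention date (VII.B.1.c) is 08/31/2024, which is 43 days later. A 6-week (42-day) second period ending on 08/31/2024 must start by 7/20/2024.

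**The case against.** The strongest reply is that no stated commitment is broken. VIII.2 promises a test before losartan and does not say it happens only once. It can be read as covering whichever period contains losartan. The attached operating procedures and the consent form were not available, and either might require a repeat. Both points stand: the finding concerns what the visible schedule contains. However, no listed visit puts the wider reading into effect, and the visit 1 test alone satisfies the sentence.

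Other safeguards are real. Contraception is a condition of enrolment (VI.13), and planned pregnancy within 6 months is an exclusion that covers the 14–16 weeks of participation at minimum washout. Visit 5, where it takes place, includes staff contact about side effects and whom to call. These lower the probability, but none of them detects a pregnancy.

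The expected counts also overstate the harm. They count pregnancies, not unrecognized pregnancies exposed to losartan, and some women would notice and report a pregnancy during an 8–10 week interval. The upper end combines the highest failure rate, the longest interval at minimum washout and the largest group. Conception during the 6 weeks on losartan is equally untested in both sequences, and a test before period 2 does not address it.

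The early hand-out text uses visit numbers that do not fit the seven-visit list and may be left over from an older schedule, so it is uncertain whether that option is still used. The main gap does not depend on it.

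Finally, unless the last intervention date is extended, a change at this stage would reach few or no further women. That limits its practical benefit but not the correctness of the point.

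**Conclusion.** The concern holds and should be fixed. On the visible schedule, the only pregnancy test is 0–2 weeks old at the first losartan dose in one randomized sequence and at least 8–10 weeks old in the other. These intervals follow from the document alone. For placebo-first women the test no longer serves the purpose VIII.2 gives for it, and detection depends on the woman recognizing and reporting a pregnancy.

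The absolute risk is low: roughly 0.008 to 0.16 expected pregnancies in the gap across the trial, under the assumed failure rates and 1:1 allocation. The case for acting rests on the severity of the harm and the small cost of preventing it. Confidence is medium, because a repeat test may be required in material that was not available.

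**What to change.** For every subject, whichever sequence she is in, require a negative urine pregnancy test and re-confirmed contraception at visit 5, after washout and before period-2 pills are dispensed. Applying this to everyone keeps the blind.

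If pills are handed out early at the first experimental visit, a test at that visit would still be at least 2 weeks old when dosing starts. In that case, require a negative home test on the day of the first period-2 dose or the day before, reported to staff, with no dose taken until it is reported. Otherwise, remove the early hand-out option.

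If the operating procedures already require a repeat test, say so in the visit 5 description.

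The cost is one inexpensive test for each woman who reaches period 2 (about 10–15, at most 20) and a short IRB modification. Sample size, outcomes and blinding are unchanged.

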Does this study have a plan to have an individual or committee review combined data from all subjects on a periodic basis (such as summary or aggregate safety and/or efficacy data)?

Yes

VIII.4

Describe the plan to review combined data from all subjects, such as summary or aggregate safety and/or efficacy data. Include the following:

- **Describe what data will be summarized and reviewed**
- **Describe how frequently data will be reviewed.**

The local Data Safety Monitoring Board performs bi-annual reviews of the study protocol, subject enrollment information, and aggregate data collected to that point. The DSMB does not have access to individual identification of subjects. The DSMB then makes recommendations regarding the progress of the study.

VIII.5

Will overall safety monitoring be performed by individual(s)/committee at The University of Iowa. (NOTE: If this study involves more than minimal risk, in most cases these should be individuals who are not members of the study research team.)?

Yes

VIII.6

List names:

[name]; [name]; [name]

VIII.7

Will overall safety monitoring be performed by individuals or committee not associated with The University of Iowa (such as a study Data Safety Monitoring Board)?

No

IX. Benefits

IX.1

What are the direct benefits to the subject (do not include compensation or hypothesized results)?

The study procedures and/or findings do not provide direct benefits to the subjects participating in the study. Subjects receive a medical screening that could inform them about their health. They learn their blood pressure and blood cholesterol levels. This is important knowledge. High blood pressure and blood cholesterol contribute to many serious health problems. We advise those with high blood pressure or blood cholesterol to follow-up with a health care provider. They also learn of the connection between preeclampsia and cardiovascular disease.

IX.2***What are the potential benefits to society in terms of knowledge to be gained as a result of this project?***

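### The side-effect log admits only mild, tolerable, expected effects and no visit collects it, so a complete side-effect record by treatment period is not assured

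*Combined protocol and SAP*

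**What the plan says.** The handling of losartan side effects is in VIII.2, under the risks of losartan treatment.

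- **Log.** The instruction begins "If the subject experiences any mild but tolerable expected side effects such as cold symptoms, mild dizziness, back pain, or diarrhea" and continues: "they will be asked to keep a log of these including the date, the duration, and the severity". Severity is entered by "rating on a scale of 1 (mild) to 10 (severe/intolerable".
- **Worse effects.** "If the subject feels the side effects are uncomfortable or intolerable, then they will be instructed to call the Research Associate". Staff then follow a skip-or-discontinue sequence. For a woman who discontinues: "The subject will be withdrawn from the study procedures but will be followed up as necessary".
- **Emergencies.** "if a subject experiences side effects that are life threatening, the subject will be instructed to call 911".

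VII.E.6 describes the visits. At visits 2 and 5 women receive pills, are told about possible side effects and are told whom to contact with problems. At visits 3 and 6 they are fitted with the blood pressure monitor. At visits 4 and 7 they return the monitor, give blood and urine, and undergo pulse wave velocity and microdialysis.

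Among the losartan risks, VIII.1 lists "Swelling in feet, ankles, or hands, or unexplained weight gain". In VIII.4 the monitoring board "performs bi-annual reviews of the study protocol, subject enrollment information, and aggregate data collected to that point". XI.1 lists no side-effect analysis.

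**The concern.** Followed as written, the log fills with the least troublesome effects. The uncomfortable, severe and unexpected ones depend on whatever staff happen to note during a call. A log that no visit collects may also stay with the participant.

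This is a double-blind crossover, so each woman who completes it provides her own placebo comparison. That comparison is useful only if the same kinds of effect are recorded in the same way in both periods. With so few women, each unrecorded event is a noticeable share of the safety information. The primary outcome, cutaneous vascular conductance, is not affected.

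**Working it through.** The documents give no side-effect rate, difference or power, so there is no stated figure to reproduce. The check is mainly a comparison of sections.

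**Step 1: what is written down (VIII.2 and VII.E.6).**

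| Kind of effect | Stated route | Stated written record |
|---|---|---|
| Mild, tolerable, expected | Participant's log | Yes: date, duration, severity |
| Tolerable, unexpected | Contact given at visits 2 and 5 | None stated; outside the log's entry rule |
| Uncomfortable or intolerable | Telephone call, then skip or discontinue | None stated |
| Life-threatening | 911 | None stated |

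One of four kinds has a stated record. A scale ending at severe or intolerable has no purpose if only mild, tolerable effects may be entered, so the two parts of VIII.2 must be reconciled.

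**Step 2: whether the log comes back.** None of visits 2 to 7 mentions handing out, collecting or reviewing a log, or asking about losartan side effects. VII.E.4 asks for all questionnaires and written assessments; three are listed, and the log is not one of them. VII.B.11 says there is no separate written protocol. Weight gain is a named losartan risk in VIII.1, but VII.E.6 lists a weight measurement only at visit 1, so later detection depends on the woman reporting it.

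**Step 3: women who stop early.** From XI.2, 20 enrolled − 5 ineligible = 15 starting, and 15 − 5 dropouts = 10 completing. Dropouts are 5/15, or one third. Their reasons are not given. A woman who withdraws for side effects has no stated visit at which to hand in a log, and VII.E.7 says follow-up is not required.

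**Step 4: what a complete record could show.** Assume side-effect rates on losartan and placebo that are independent within a woman, and an exact two-sided McNemar test at 0.05. The smallest significant result with all discordant pairs in one direction needs 6 pairs: 2 × 0.5^5 = 0.063, and 2 × 0.5^6 = 0.031. For 30% against 10%, the discordant probabilities are 0.30 × 0.90 = 0.27 and 0.10 × 0.70 = 0.07.

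| Assumed rates (losartan vs placebo) | Power, 10 women | Power, 15 women |
|---|---|---|
| 30% vs 10% | 2% | 9% |
| 40% vs 10% | 8% | 26% |
| 50% vs 10% | 19% | 49% |
| 60% vs 10% | 37% | 72% |

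Fifteen is an upper limit, since a paired comparison needs both periods. The chance of seeing at least one event among 10 women, 1 − (1 − p)^10, is 40%, 65% and 89% for true rates of 5%, 10% and 20%. The value of the log is therefore descriptive.

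**The case against.** The strongest reply is that information reaches the team by other means. Women are told whom to contact with problems of any kind, so a reader who infers that unexpected effects have no route at all would be wrong; what is missing is a recording step. Calls and discontinuations come to staff. Blood chemistry, urine protein and 24-hour blood pressure are obtained in both periods. Log entries carry dates and could be matched to treatment after unblinding. So the documents do not support the stronger reading that a losartan difference would go unseen. That reply stands, with one limit: the end-of-period measurements follow six weeks of treatment, and a woman who withdraws sooner has none stated.

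A reader might also infer that the monitoring board sees losartan and placebo merged, and that any difference is thereby halved. VIII.4 does not say so. Aggregate there can simply mean combined over subjects; the only stated restriction is on individual identity, and no section links the log to the board. The section is silent on a treatment split, and silence does not establish pooling.

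The telephone call can be read as escalation of effects already logged, which would explain the wide scale. That covers effects that start mild and worsen. It does not cover those that are unexpected or uncomfortable from the outset.

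Finally, comparing side effects is not a study aim, and attachments not available here, including the standard operating procedures, may describe recording. VIII.2 cites that document for physician oversight. These points limit the weight of the concern but do not resolve the contradiction in VIII.2.

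**Conclusion.** The concern holds in a limited form. VIII.2 states an entry rule that conflicts with its own scale and leaves three of four kinds of side effect without a stated written record. VII.E.6 gives no step for retrieving the log. A complete record by treatment period is therefore not assured, which is less than saying that differences would be missed.

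The conclusion rests on the sections available and assumes that no attachment supplies the missing steps. The power figures rest on assumed rates and independence between periods; they show only that a full log would support description and, except for very large differences, not a formal test. The primary analysis is untouched.

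**What to change.** In VIII.2, reconcile the entry rule with the scale: have women log every side effect regardless of severity or expectedness, and have staff enter phoned effects and side-effect withdrawals on the same dated form. The existing rules on calling, skipping and discontinuing are outside this change.

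In VII.E.6, add collection and review of the log at visits 4 and 7 and at withdrawal. Identify these as the experimental visits that end each treatment period, because the closing paragraph of that section numbers visits differently. In XI.1, add a descriptive table of side effects and side-effect withdrawals by treatment period, without a formal test.

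VII.B.1.c gives 08/31/2024 as the last visit date. For women already finished, the equivalent step is to retrieve existing logs and call notes and tabulate them by period.

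The cost is a revised form and a few minutes at visits already scheduled, with no added visits, tests or participants.

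### The skip-one-dose-and-resume rule in VIII.2 has no stated exception for the allergic reaction that VIII.1 lists as a losartan risk

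*Combined protocol and SAP*

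**What the plan says.** VIII.1 names the risk: "Subjects could have a mild or severe allergic reaction including hives; difficult breathing; swelling of the face, lips, tongue, or throat". The only response given there is to exclude women whose losartan allergy is already known, which matches the exclusion criterion in VI.13. The neighboring entries for low blood pressure and for edema each add that the problem can be treated by stopping the drug. The allergy entry does not.

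VIII.2, under Risks Associated with Losartan Treatment, sorts side effects by severity:

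- Life-threatening: "if a subject experiences side effects that are life threatening, the subject will be instructed to call 911".
- Expected and tolerable: "mild but tolerable expected side effects such as cold symptoms, mild dizziness, back pain, or diarrhea" are to be logged and scored for severity.
- Uncomfortable or intolerable: "If the subject feels the side effects are uncomfortable or intolerable, then they will be instructed to call the Research Associate" or another named team member. That person "will instruct the subject to skip the next dose and if the symptoms/side effects have resolved at time of next dose", 24 hours later, has her take it.

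The stopping condition is: "If symptoms do not resolve or worsen at time of next scheduled dose, the subject will be instructed to discontinue the treatment". Consultation with a further named person is available when judged necessary. VIII.2 opens with a note that "All investigational substances used in these protocols are used with general Physician Oversight" and refers to an attached Standard Operating Procedures document.

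**The concern.** The branches are defined by how severe the effect is and how the woman feels about it, not by what kind of reaction it is. For dizziness or diarrhea, waiting a day and trying again is reasonable. For a suspected drug allergy, resolution off the drug does not show that the next tablet is safe. That last statement is ordinary clinical judgment and is not taken from the documents.

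The group at issue is narrow: a woman whose reaction is not life-threatening, who phones, whose reaction clears by the next scheduled dose, and whom staff restart without consulting a physician. For her, the written rule permits re-exposure with no required review. VII.D.29 describes the participants as healthy, and IX.1 states that the study procedures and findings bring them no direct benefit. The documents therefore give no therapeutic reason to accept that re-exposure.

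**Working it through.** No figure in the plan bears on this point. The check is to take one case, hives or lip swelling that is not life-threatening, through each branch of VIII.2, and then to look for an exception elsewhere in the available text.

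**Step 1. Life-threatening branch.** By definition it does not apply to this case. Where it does apply, the instruction ends with the 911 call. Nothing says whether study drug may be taken afterwards.

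**Step 2. Logging branch.** It covers mild, tolerable, expected effects, and none of its four examples is allergic. If a woman placed mild, tolerable hives here, she would only record them: no call and no skipped dose.

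**Step 3. Skip-and-resume branch.** The result depends on what the words for side effects refer to.

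| Reading | What the branch covers | Result for a reaction that clears |
|---|---|---|
| Literal | Any side effect felt to be uncomfortable or intolerable | Skip one dose, then take the next tablet |
| Narrower | Only the expected effects named just before | No branch applies; VIII.2 gives no dosing instruction |

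**Step 4. Stopping condition.** It requires symptoms that persist or worsen at the next scheduled dose. A reaction that has cleared does not meet it. Neither reading therefore produces a stop.

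**Step 5. Other safeguards in the text.**

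- VI.13 and VIII.1 exclude known allergy. This acts at entry and is not written as a rule for a first reaction on treatment.
- Consultation in VIII.2 is discretionary. No trigger is defined, and allergy is not named.
- General physician oversight is stated, but VIII.2 does not make physician review a condition of the next dose.
- Under VIII.4 the Data Safety Monitoring Board reviews aggregate data bi-annually, so it cannot act between one tablet and the next.
- VIII.2 has staff watch constantly for itching, redness and swelling while microdialysis fibers are in place. The tablets are taken away from the site over six weeks, so that observation does not cover them.

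**Step 6. Is review before the next dose feasible?** VII.E.6 specifies one tablet a day. Counting from the last tablet taken, the skipped dose falls at hour 24 and the resumed dose at hour 48. A call at hour 0 leaves 48 − 0 = 48 hours, and a call at hour 24 leaves 48 − 24 = 24 hours. A physician therefore has 24 to 48 hours to review the case by phone.

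**The case against.** The best reply is that the narrower reading is the natural one. The skip-and-resume sentence follows directly on the list of expected effects, and the log scale runs from mild to intolerable. The sense may simply be that if those same effects become hard to bear, she should call. VIII.1 also lists allergic reaction under its own heading, apart from the common effects. On that reading, no text tells staff to restart a woman with hives. This stands as a fair reading, but it leaves VIII.2 silent on a risk that VIII.1 names, and it does not supply a stop.

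Second, the handling of such reactions may sit in the attached Standard Operating Procedures document, or in the instructions given when tablets are collected (VII.E.6, Visits 2 and 5). Neither could be checked. This also stands, and it limits the point to the visible text of VIII.2.

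Third, other protections exist: the 911 instruction, discontinuation for persisting or worsening symptoms, optional consultation, and each woman's freedom to leave at any time (VII.D.29). Sensible staff may well stop the drug anyway. These narrow the group at risk, but none makes review a condition of the next tablet.

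Two stronger inferences are tempting. A reader might conclude that the plan requires rechallenge after an allergic reaction. The text does not support that, because the wording is open to the narrower reading and consultation is available. A reader might also count the tablets left in a six-week period and present that number as the size of the harm. A count of later tablets does not measure harm: the largest counts arise when the reaction never comes back.

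**Conclusion.** The point holds for the visible text of VIII.2. The rule for uncomfortable or intolerable effects is not limited by type of reaction and has no allergy exception. Read literally, it leads to another tablet after a non-life-threatening reaction that clears, without required physician review. Read narrowly, it gives no dosing instruction for that case.

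The documents give no allergy rate. The event should be rare, and no probability or tablet count is claimed. The tablet may be losartan or placebo, and VIII.2 acknowledges that one of the people who may take the call is blinded, so the gap applies in both treatment periods.

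The conclusion assumes that the unavailable attachment and pick-up instructions do not already contain a stop. If they do, what remains is a missing cross-reference. A reader should not infer that the trial has no protection against allergic reactions; the documents do not support that. Priority: a minor safety fix.

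**What to change.** Add to VIII.2 and to the medication pick-up instructions:

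- Hives, swelling of the face, lips, tongue or throat, or difficulty breathing are exempt from skip-and-resume, including after a 911 call.
- The woman stops study drug and calls at once, even if she finds the reaction tolerable.
- She takes no further dose in either period unless the overseeing physician has reviewed the case and cleared it. Otherwise she discontinues.
- Expected effects such as runny nose, sneezing, mild dizziness, back pain and diarrhea stay under the current rule.

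The reactions should be listed by name. A general phrase such as any suspected allergic reaction could sweep in the runny nose and sneezing that VIII.1 gives as common losartan effects. If the attached procedures already contain this rule, citing them in VIII.2 is enough.

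The cost is a few sentences, a few physician calls and possibly an occasional extra withdrawal, which could occur on placebo. No visits or participants are added. XI.2 already allows for about 5 dropouts (20 − 5 screened out − 5 dropouts = 10 completers), so an extra loss may fall within that allowance. If it did not, and completers fell from 10 to 9, the standard error of the within-woman difference would grow by a factor of √(10/9) = 1.054, about 5.4%, with the standard deviation unchanged. Only reactions that cleared could add withdrawals, because the current rule already withdraws women whose symptoms persist or worsen.
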